5.3.1 Baseline

For Safety Analysis, the following conventions will be applied for the definition of baseline:

For the Safety Population baseline will be the last value prior to first administration of ARCT-021 in Study ARCT-021-02.

For the Longitudinal Safety Population baseline will be the last value prior to first administration of ARCT-021 in either the ARCT-021-01 or ARCT-021-02 study (whichever study represented the first ARCT-021 vaccination)

For the Immunogenicity Analysis, Immunogenicity baseline will be defined as:

- Cohort 1a and 1b: Last value prior to or on Day 1 of ARCT-021-02
- Cohorts 2 (A to D2) and 2 (E to H): Last value prior to or on Day 1 of ARCT-021-01

For assessments collected during the screening period as well as on Day 1, the Day 1 value will be used as baseline. If more than one assessment exists within a single visit window, the value closest to the protocol study visit will be used for summary and analysis purposes. If more than one equidistant to the protocol study visit assessments exists, then earliest of these values will be used for summary and analysis purposes. Data from all assessments will be listed.

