10.3 Definition of Baseline

For the Safety Population baseline will be the last value prior to first administration of ARCT-021 in Study ARCT-021-02.

For the Longitudinal Safety Population baseline will be the last value prior to first administration of ARCT-021 as it occurred in either the ARCT-021-01 or ARCT-021-02 study.

For the Immunogenicity Population: baseline will be defined as follows.

- Baseline for Cohort 1a and 1b: Day 1 of ARCT-021-02 study
- Baseline for Cohort 2a, 2b, 2c, 2d: Day 1 of ARCT-021-01

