14 APPENDICES

APPENDIX 1: SCHEDULE OF ASSESSMENTS

Appendix 1: Schedule of Assessments

1. Screening

Subjects who Received Placebo or a Single Injection of ARCT-021 in Parent Study

Study Week/Day	D -28 to D -1
Visit Window (Days)	0
Informed Consent	X
Inclusion/Exclusion	X
Body Weight	X
Physical Exam ¹	X
Vital Signs ²	X
Pregnancy Test ³	X
Chemistry Panel	X
Hematology	X
Coagulation	X
HbA1c	X
Urinalysis ⁴	X
Immunogenicity ⁵	X
Drug/Alcohol Screen ⁶	X
SAE, CESI, NOCD and MAAE ⁷	X
Concomitant Medications and Procedures ⁸	X
SARS-CoV-2 questioning ⁹	X

1 Full physical exam

2 BP, HR, RR, temp

3 Women who are not surgically sterile or post-menopausal. Dipstick acceptable

4 Dipstick test per local procedures. If abnormal send sample to laboratory for microscopy.

5 This is only PRNT50 for the screening visit

6 Urine test.

7 SAE, CESI, NOCD and MAAE that occurred since completion of the Parent Study and screening for this study will be recorded. For subjects that received ARCT-021 in the Parent Study, these will be entered as SAE/CESI/MAAE in the EDC. For subjects that received placebo in the Parent Study these will be recorded as medical history.

8 Concomitant medications and procedures since completion of the Parent Study and screening for this study will be recorded for all subjects.

9 Subjects will be questioned about symptoms of COVID-19 and exposure to confirmed COVID-19 or confirmed SARS-CoV-2 infection cases amongst household contacts, friends, work contacts and other contacts.

Subjects who Received Two Injections of ARCT-021 in Parent Study

Study Week/Day	D -28 to D -1
Visit Window (Days)	0
Informed Consent	X
Inclusion/Exclusion	X
Body Weight	X
Physical Exam ¹	X
Vital Signs ²	X
SAE, CESI, NOCD and MAAE ³	X
Concomitant Medications and Procedures ⁴	X
SARS-CoV-2 questioning ⁵	X

- 1 Full physical exam (assessment of heart, lungs, abdomen, eyes, ears, nose and throat, head and neck, musculoskeletal, lymphatic, injection site, dermatologic, neurologic, extremities)
- 2 BP, HR, RR, temp
- 3 SAE, CESI, NOCD and MAAE that occurred since completion of the Parent Study and screening for this study will be recorded
- 4 Concomitant medications and procedures since completion of the Parent Study and screening for this study will be recorded
- 5 Subjects will be questioned about symptoms of COVID-19 and exposure to confirmed COVID-19 or confirmed SARS-CoV-2 infection cases amongst household contacts, friends, work contacts and other contacts.

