4.4 Data to be Evaluated at This Interim Analysis

- Safety data will be available for all participants in Cohorts 1 and 2 (see Section 5.2 for description of cohorts).
 - For participants in Cohort 1a, safety data will be presented from Day 1 in Study ARCT-021-02 up to the data cut point for this interim analysis. Any safety data prior to Day 1 in this study will have been captured in the EDC as medical history.
 - For participants in Cohorts 1b and 2, safety data will be presented from the time of exiting the Parent Study (ARCT-021-01) up to the data cut point for this interim analysis. For participants in Cohort 1b, the safety data from the time of exiting the parent study up to Day 1 in Study ARCT-021-02 will be presented separately to the safety data following Day 1 (as participants receive an additional dose of study vaccine on Day 1).
- Immunogenicity data is not yet available for all assays/all cohorts. The data that will be evaluated at this interim is as follows (Table 2):
 - For Participants in Cohort 1a, immunogenicity data from Day 1, Day 29 and Day 57 in Study ARCT-021-02 (i.e., the only time points for which immunogenicity data is available for this cohort in ARCT-021-02) will be presented.
 - For participants in Cohorts 1b:
 - Immunogenicity data from the Parent Study for tests using the same assays as being performed in ARCT-021-02 is available only for participants in Cohorts 1b (B), 1b (D1), and 1b (D2). For these participants the Parent Study data will be presented together with the data from Day1, Day 29 and Day 57 in Study ARCT-021-02 (i.e., the time points for which immunogenicity data is available for these cohorts in ARCT-021-02). For all other participants in Cohort 1b, only immunogenicity data from Day1, Day 29 and Day 57 in Study ARCT-021-02 will be presented.
 - The proportion of participants seroconverting for neutralizing antibodies and binding antibodies against the SARS-CoV-2 Spike glycoprotein and against receptor binding domain of the SARS-CoV-2 spike glycoprotein will be assessed at Day 29 and Day 57. This is an additional analysis to those specified in the protocol.

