5.3.2 Study Day in Study ARCT-021-02

For Adverse events, Study day will be determined based on actual number of days since study Day 1. Study Day 1 will be identified from the CRF. For Cohort 1, it will be the day of vaccination. Study day for any given date will be:

- Given Date – Study Day 1 + 1 for dates on or after date of Study Day 1.
- Given Date – Study Day 1 for dates before date of Study Day 1.

For all immunogenicity data, the Study Day will be based on the nominal study day as captured in the CRF. For participants that received their first dose of ARCT-021 in the Parent study, nominal day since Day 1 in the Parent Study will also be displayed, as follows:

- For cohorts 1b (A to D2) and 2 (A to D2) Day 1 in Study ARCT-021-02 = Day 147 after Day 1 in the Parent Study, calculated as follows:
 - The time enrolled in the Parent Study is 57 days and the time between Parent Study and Day 1 in Study ARCT-021-02 is nominally 90 Days. Therefore, Day 1 in Study ARCT-021-02 is $57 + 90 = 147$ days after Day 1 in the Parent Study
- For cohorts 2 (E to H) Day 1 in Study ARCT-021-02 = Day 175 after Day 1 in the Parent Study, calculated as follows:
 - The time enrolled in the Parent Study is 85 days and the time between Parent Study and Day 1 in Study ARCT-021-02 is nominally 90 Days. Therefore, Day 1 in Study ARCT-021-02 is $85 + 90 = 175$ days after Day 1 in the Parent Study

Based on the above, in the Immunogenicity tables the visit name (when they are shown) will be displayed showing the nominal day from parent study within parenthesis. The nominal days will depend on the cohort and they will be as follows:

Table 3: Label for reporting Visit Days in safety and immunogenicity when needed.

Visit name in Protocol	Cohort			
	1a	1b	2 (A-D2)	2(E-H)
Day 1	Day 1	Day 1 (147)	Day 1 (147)	Day 1 (175)
Day 29	Day 29	Day 29 (175)	Day 29 (175)	Day 29 (203)
Day 43	Day 43	Day 43 (189)	Day 43 (189)	Day 43 (217)
Day 57	Day 57	Day 57 (203)	Day 57 (203)	Day 57 (231)
Day 85	Day 85	Day 85 (231)	Day 85 (231)	Day 85 (259)

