5.4 Handling of Dropouts or Missing Data

Due to the exploratory nature of this study and the lack of statistical testing, missing data will not be imputed. Values that are below the level of quantification will be recoded to zero for analysis purposes, with the exception of antibody titers which will be recoded to LLOQ/2.

For participants who received an off-study vaccine, Safety and Immunogenicity reports will be censored at date of first dose of off-study vaccine. Safety data after off-Study vaccine will be reported separately.

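### SAP 5.3.1 widens the Cohort 1a/1b immunogenicity baseline without declaring it, so in three booster sub-cohorts a missing Day 1 result could be filled by a parent-study value nominally 90 days old

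*SAP*

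**What the plan says.** Protocol 10.3 ties the immunogenicity baseline of the participants dosed in this study to one visit: "Baseline for Cohort 1a and 1b: Day 1 of ARCT-021-02 study". SAP 5.3.1 replaces this with "Cohort 1a and 1b: Last value prior to or on Day 1 of ARCT-021-02". It sets no limit on how far back the value may lie and does not require it to come from an ARCT-021-02 sample. It adds a precedence rule: "For assessments collected during the screening period as well as on Day 1, the Day 1 value will be used as baseline".

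SAP Section 4 is where departures from the protocol analyses are set out. It covers cohort names, timepoint grouping, the binding assay, the seroconversion definition and the data available. Section 4.3 points to 5.3.1 for baseline, but nowhere says that the baseline rule differs from the protocol.

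On which samples exist, the screening footnote in Protocol Appendix 1 reads "This is only PRNT50 for the screening visit". SAP 7.2 names the interim assays as pseudovirus neutralisation and MSD multiplex binding IgG. SAP 4.4 says that, among the booster participants, parent-study data by these assays "is available only for participants in Cohorts 1b (B), 1b (D1), and 1b (D2"). SAP 5.4 says "missing data will not be imputed".

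**The concern.** Baseline is the denominator of every GMFR. It now also decides every seroconversion result, because SAP 4.3 drops the protocol's titer-above-20 criterion for baseline-seronegative participants and uses fold rise from baseline alone.

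In Cohort 1b the fold rise is meant to describe the response to the dose given in this study, so the denominator should be the antibody level just before that dose. A sample from the end of the parent study does not measure that. Cohort 1b participants enter because they were PRNT50 negative at screening, so a fall after parent Day 57 is plausible for at least some of them. An older, higher value would make the booster response look smaller than it was.

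The fallback would also be uneven. It could operate only in sub-cohorts that have same-assay parent data, so identical gaps would be treated differently across prior-dose sub-cohorts that will be read side by side.

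**Working it through.** **1. Which earlier value could the rule select?**
- Screening: PRNT50 only (Protocol Appendix 1), which is neither interim assay. No archived serum is scheduled at screening.
- Parent study, same assays (SAP Table 2): 1b (B) has Day 57 only; 1b (D1) and 1b (D2) have Days 1, 29, 43 and 57; 1b (A) and 1b (C) have none; 1a has none.
- So the last same-assay value before Day 1 is parent Day 57 in B, D1 and D2. There is nothing to carry forward in 1a, 1b (A) or 1b (C).

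**2. How old would it be?** SAP 5.3.2 states that "the time between Parent Study and Day 1 in Study ARCT-021-02 is nominally 90 Days" and that "Day 1 in Study ARCT-021-02 = Day 147 after Day 1 in the Parent Study".
- Plan's own figure: 57 + 90 = 147, reproduced.
- Age of the parent Day 57 value: 147 − 57 = 90 nominal days.
- SAP 7.2 labels Day 29 as Day 176 for the single-dose Cohort 2 groups, where Table 3 has 175. That implies Day 1 = 176 − 28 = 148 and an age of 148 − 57 = 91 days. The one-day discrepancy does not affect the point.

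**3. Effect on one affected participant.** Let w be the ratio of the parent Day 57 titer to the true Day 1 titer. No document gives w.
- Observed fold rise = true fold rise / w.
- At the 4-fold threshold, the classification changes only if 4 ≤ true rise < 4w. For an assumed w = 2 that is 4 to below 8; for w = 4 it is 4 to below 16. Example: a true 6-fold rise with w = 2 reads as 6/2 = 3-fold and is scored as no seroconversion.
- True rises below 4-fold are not seroconversion under either baseline.
- If w = 1, for instance when both samples are below LLOQ and recoded to LLOQ/2, nothing changes. If w < 1, the fold rise would be overstated.

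**4. Effect on a sub-cohort GMFR.** If a fraction m of participants take the parent value with a common w, the SAP 7.2 definition gives observed GMFR / true GMFR = w^(−m). Both m and w are assumptions, and the figures are illustrative only:

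| m | w = 1 | w = 2 | w = 4 | w = 8 |
|---|---|---|---|---|
| 0 | 1.00 | 1.00 | 1.00 | 1.00 |
| 5% | 1.00 | 0.97 | 0.93 | 0.90 |
| 10% | 1.00 | 0.93 | 0.87 | 0.81 |
| 20% | 1.00 | 0.87 | 0.76 | 0.66 |

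The same factor separates the SAP rule from a Day 1-only rule if affected participants have the same true fold rise as the others.

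**5. Do other SAP passages close the gap?** The precedence sentence in 5.3.1 decides between two values when both exist; it is silent when Day 1 is absent. The no-imputation statement in 5.4 conflicts with a carried-forward baseline, but it does not mention 5.3.1 or limit it. No passage says that a parent-study value is to be used, and none excludes it.

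**The case against.** The strongest reply is that nothing may ever trigger the rule. Day 1 immunogenicity is a scheduled pre-dose sample with a zero-day window. SAP Table 2 marks Day 1 as available for 1a and every 1b sub-cohort, and Day 1 serum is archived, so a failed assay might be repeated. Wherever a Day 1 value exists, the two definitions agree. In addition, the only look-back that 5.3.1 mentions is the screening period, 5.4 points away from substitution, and 4.4 says only that the parent data will be shown alongside this study's data. The analysis is a descriptive interim without hypothesis tests, and all assessments will be listed, so a substituted baseline could be traced.

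Much of this stands. It makes the effect conditional and possibly nil. It does not repair the wording. Table 2 speaks for sub-cohorts, not individuals, and SAP 5.1 has the data pulled while queries are still open. For the interim assays no screening value exists, so in practice the words about earlier values reach only the parent study.

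A reader might go further and infer that the SAP orders missing Day 1 results to be replaced and that the booster fold rise is therefore misstated. The documents do not support that: replacement follows from a literal reading, not from an express instruction, and no missing Day 1 result is reported. Nor do they support a percentage loss in GMFR. They give no waning factor and no sub-cohort sizes, and spreading the 106 potential participants evenly over sub-cohorts would be guesswork because entry to 1b depends on PRNT50 status at screening.

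**Conclusion.** The point holds as a conditional defect. SAP 5.3.1 departs from Protocol 10.3 without declaring it. Read literally, it permits a same-assay parent-study baseline, nominally 90 days old, for a participant in 1b (B), 1b (D1) or 1b (D2) whose Day 1 result is missing. It permits none in 1b (A) or 1b (C), and it sits in tension with SAP 5.4.

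The direction, an understated fold rise, rests on the assumption that antibody fell between parent Day 57 and Day 1. The size depends on how many Day 1 results are missing and on the waning factor; the documents give neither, and the effect is zero if none is missing. No type I error or power is involved. What is at stake is the accuracy and comparability of descriptive secondary summaries in an interim prepared for a regulatory filing.

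**What to change.** In SAP 5.3.1, restore the protocol rule: for Cohorts 1a and 1b the immunogenicity baseline is the pre-dose Day 1 result of ARCT-021-02 by the same assay. If that result is missing, the participant's GMFR contribution and seroconversion status are missing, the available titers or concentrations still enter the GMT/GMC, and the number missing is reported by sub-cohort and assay. If the sponsor prefers to keep the wider rule, it should be listed in Section 4 with a stated look-back limit and reconciled with 5.4.

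SAP 5.1 bars changes once the data are pulled. If that has happened, make the correction in the next SAP, and state in the report how many Cohort 1b baselines, if any, came from the parent study.

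The cost is a few lines of text. The downside is that any participant without a Day 1 result drops out of the fold-rise and seroconversion summaries; everyone with a Day 1 result is unaffected.

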5.3.2 Study Day in Study ARCT-021-02

For Adverse events, Study day will be determined based on actual number of days since study Day 1. Study Day 1 will be identified from the CRF. For Cohort 1, it will be the day of vaccination. Study day for any given date will be:

- Given Date – Study Day 1 + 1 for dates on or after date of Study Day 1.
- Given Date – Study Day 1 for dates before date of Study Day 1.

For all immunogenicity data, the Study Day will be based on the nominal study day as captured in the CRF. For participants that received their first dose of ARCT-021 in the Parent study, nominal day since Day 1 in the Parent Study will also be displayed, as follows:

- For cohorts 1b (A to D2) and 2 (A to D2) Day 1 in Study ARCT-021-02 = Day 147 after Day 1 in the Parent Study, calculated as follows:
 - The time enrolled in the Parent Study is 57 days and the time between Parent Study and Day 1 in Study ARCT-021-02 is nominally 90 Days. Therefore, Day 1 in Study ARCT-021-02 is $57 + 90 = 147$ days after Day 1 in the Parent Study
- For cohorts 2 (E to H) Day 1 in Study ARCT-021-02 = Day 175 after Day 1 in the Parent Study, calculated as follows:
 - The time enrolled in the Parent Study is 85 days and the time between Parent Study and Day 1 in Study ARCT-021-02 is nominally 90 Days. Therefore, Day 1 in Study ARCT-021-02 is $85 + 90 = 175$ days after Day 1 in the Parent Study

Based on the above, in the Immunogenicity tables the visit name (when they are shown) will be displayed showing the nominal day from parent study within parenthesis. The nominal days will depend on the cohort and they will be as follows:

Table 3: Label for reporting Visit Days in safety and immunogenicity when needed.

Visit name in Protocol	Cohort			
	1a	1b	2 (A-D2)	2(E-H)
Day 1	Day 1	Day 1 (147)	Day 1 (147)	Day 1 (175)
Day 29	Day 29	Day 29 (175)	Day 29 (175)	Day 29 (203)
Day 43	Day 43	Day 43 (189)	Day 43 (189)	Day 43 (217)
Day 57	Day 57	Day 57 (203)	Day 57 (203)	Day 57 (231)
Day 85	Day 85	Day 85 (231)	Day 85 (231)	Day 85 (259)

5.3.3 Censoring

As participants in this study have, in many instances, received a COVID-19 vaccine that was not the designated investigational vaccine (“off study vaccine”) and receipt of a similar vaccine may influence

study interpretability, data will be censored at the time of receipt of this off study vaccine. Additional data collected past that day will be referred to as: Follow-up After Receipt of Off Study Vaccine.

Censoring Day is defined as:

- Date of first Off-Study Vaccine Dose - Study Day 1 + 1 for dates on or after date of Study Day 1.
- Date of first Off-Study Vaccine Dose - Study Day 1 if both doses of Off-Study vaccine were received prior to enrollment in ARCT-021-02.

5.4 Handling of Dropouts or Missing Data

Due to the exploratory nature of this study and the lack of statistical testing, missing data will not be imputed. Values that are below the level of quantification will be recoded to zero for analysis purposes, with the exception of antibody titers which will be recoded to LLOQ/2.

For participants who received an off-study vaccine, Safety and Immunogenicity reports will be censored at date of first dose of off-study vaccine. Safety data after off-Study vaccine will be reported separately.

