	
• Mild: The event is easily tolerated by the subject and does not affect the subject's usual daily activities• Moderate: The event causes the subject more discomfort and interrupts the subject's usual daily activities• Severe: The event is incapacitating and causes considerable interference with the subject's usual daily activities 
Cases of PCR confirmed COVID-19 and PCR-confirmed or serologically confirmed asymptomatic SARS-CoV-2 infection will be recorded as Clinical Events of Special Interest (CESI). These events will not be regarded as adverse events and will be analyzed separately from safety data (Sections 9.3.7 and 9.5.5). PCR confirmed COVID-19 disease will be graded as follows:
 
• Mild: No requirement for supplemental oxygen to maintain oxygen saturation $\geq 93\%$• Moderate: Oxygen supplementation at a concentration of $< 50\%$ required to maintain oxygen saturation $\geq 93\%$• Severe: Oxygen supplementation at a concentration of $> 50\%$ or any form of mechanical ventilatory support required 
Immunogenicity
 
Immunogenicity measures include mean titer, GMT and GMFR in neutralising antibody titer to SARS CoV-2 spike protein and anti-spike protein IgG titer and the proportion of subjects seroconverting. Descriptive statistics, by assessment time point, will be used to describe these results. Statistical testing, if performed, will be prespecified in the final statistical analysis plan and will be exploratory in nature.
 
SARS-CoV-2 neutralising antibody titer will be tested using a clinical isolate of SARS CoV-2 (hCoV-19/Singapore/2/2020) in BSL-3 settings on an in vitro plaque reduction neutralisation test (PRNT) and/or pseudovirus neutralization test and/or surrogate virus neutralization test (sVNT) and/or microneutralization test. Testing using other SARS-CoV-2 isolates may also be performed.
 
Total IgG against the full-length SARS-CoV-2 recombinant spike protein and/or spike protein subunits will be assessed using an immune-Luminex and/or ELISA assay.

--	---

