10.5.6 Missing Data Handling

Due to the exploratory nature of this study and the lack of statistical testing, missing data will not be imputed. Values that are below the level of quantification will be recoded to zero for analysis purposes.

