2.2.2 Secondary Endpoints

Immunogenicity

1. Mean and geometric mean titer or concentration (GMT, GMC) and the geometric mean fold rise (GMFR) in SARS-CoV-2 neutralizing antibodies and in binding antibody against the SARS-CoV-2 Spike glycoprotein and against receptor binding domain of the SARS-CoV-2 spike glycoprotein, at multiple time points in each cohort.
2. Proportion of ARCT-021-naïve participants (Cohort 1a; see Section 5.2 for description of cohorts)

seroconverting for neutralizing antibodies and binding antibodies against the SARS-CoV-2 Spike glycoprotein and against receptor binding domain of the SARS-CoV-2 spike glycoprotein will be assessed at multiple time points.

The proportion of ARCT-021 boosted participants (Cohort 1b) seroconverting for neutralizing antibodies and binding antibodies against the SARS-CoV-2 Spike glycoprotein and against receptor binding domain of the SARS-CoV-2 spike glycoprotein will also be assessed at multiple time points. This is an additional analysis to those specified in the protocol.

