5. GENERAL CONSIDERATIONS FOR DATA ANALYSIS

As there is no comparator group, there will be no formal hypothesis testing and therefore most of the statistical summaries will be descriptive and through displays of the data.

For this interim analysis, the following conventions will be used:

- Safety data:
 - All adverse event data reported for participants in Cohort 1a prior to Day 1 of study ARCT-021-02 are handled as medical history in the ARCT-021-02 study. The site was instructed to enter all medical history and ongoing adverse events from study ARCT-021-01 as medical history in this study.
 - All adverse event data reported for participants in Cohort 1b and Cohort 2 (all

subgroups) prior to Day 1 are handled as adverse events in the ARCT-021-02 study. For Cohort 1b, adverse event data occurring since end of study participation in ARCT-021-01 are summarized as adverse events but analyzed separately from those recorded in study ARCT-021-02 for the purpose of this analysis (since these participants received study vaccine in this study). For participants in Cohort 2, adverse event data occurring since end of study participation in ARCT-021-01 will be merged with AE data from Study ARCT-021-02 for the purposes of tabular presentation (since these participants do not receive additional study vaccine in this study)

- Immunogenicity data
 - Seroconversion will be defined as a 4-fold increase from baseline (Section 5.3.1) in antibody titer/concentration. An additional analysis at a threshold of 2-fold increase from baseline will also be performed.
 - Seropositivity at participant level for any timepoint (including baseline) is defined as a detectable level above LLOQ at that time point.

The summary statistics will consist of absolute and relative frequencies (percentages) for categorical variables and mean, median, standard deviation, minimum, maximum as well as number of non-missing observations will be used for discrete and continuous variables. For titers, geometric mean and 95% confidence intervals (CIs) will also be provided, as well as the percent geometric coefficient of variation (%GCV).

Summary statistics will also be provided for change from baseline using mean, median, standard deviation, minimum and maximum as well as the number of non-missing observations. Where applicable, the percentage change from baseline will be provided. For titer, geometric mean fold rise and 95% CIs will also be provided, as well as the %GCV.

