7.3.1.1 Binding Antibodies

Endpoint titers of Binding antibodies, by participant, and time point, will be listed for each of the 3 tests listed below. Mean titer, GMC, GMFR, 95% CIs, median, minimum, and maximum values and number and percent of participants seroconverting will also be summarized by cohort/sub-cohort and time point for:

- Anti-spike glycoprotein
- Anti-RBD
- Nucleocapsid

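### The protocol's zero recode for below-LLOQ results cannot be used with geometric means or fold rises, and the interim SAP's LLOQ/2 repair does not clearly reach binding-antibody concentrations

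*SAP*

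**What the plan says.** **Protocol.** Section 10.5.6 has one rule and no exception: "Values that are below the level of quantification will be recoded to zero for analysis purposes". The secondary endpoints in section 1.2.2 are mean titer, GMT and GMFR for neutralising antibody and anti-spike IgG, and the proportion of vaccine-naive subjects who seroconvert. Section 10 leaves full details to a SAP to be finalised before final database lock.

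**SAP.** By its introduction, the SAP supplied covers an interim analysis. Section 5.4 repeats the zero rule and adds an exception: "with the exception of antibody titers which will be recoded to LLOQ/2". The exception is not limited to neutralising assays, and it does not mention concentrations.

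**Usage of the two words in the SAP.**
- *Kept apart:* section 2.2.2 pairs titer with GMT and concentration with GMC. Section 5 says "Seroconversion will be defined as a 4-fold increase from baseline (Section 5.3.1) in antibody titer/concentration". Section 7.3 gives the anti-nucleocapsid cut-off as a concentration in AU/ml.
- *Merged:* section 7.3.1.1 says "Endpoint titers of Binding antibodies, by participant, and time point, will be listed for each of the 3 tests listed below", the three being anti-spike, anti-RBD and nucleocapsid, and then plans "Mean titer, GMC, GMFR, 95% CIs, median, minimum, and maximum values" for the same data. Section 5 says "For titers, geometric mean and 95% confidence intervals (CIs) will also be provided", with no parallel sentence for concentrations. The protocol synopsis also speaks of "anti-spike protein IgG titer and the proportion of subjects seroconverting".

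**The concern.** GMT, GMC and GMFR are means of logarithms. The logarithm of zero does not exist, and neither does a ratio to a zero baseline. Under the protocol rule the software must therefore fail, return zero, or leave out the affected participants. Leaving them out removes the lowest values and pushes the geometric mean upwards.

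The SAP's exception shows that LLOQ/2 was judged necessary for titers. If concentrations fall outside it, the same difficulty remains for all three binding assays in an interim that, by SAP section 4, supports a regulatory filing.

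Fold-based endpoints are the most exposed. By SAP 5.3.1, the baselines of Cohorts 1a and 2 precede any ARCT-021 dose. Below-LLOQ baselines are plausible there, although the documents do not say how common they are.

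**Working it through.** **Inputs.** The formulas come from SAP 7.2: GMT is the antilog of the mean of log10(Y), and GMFR the antilog of the mean of log10(Y/B), with Y the post-dose and B the baseline result. The recode rules come from protocol 10.5.6 and SAP 5.4. The documents give no LLOQ and no share of results below it, so both are assumed here. The plan states no figure on this point to reproduce.

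**1. Geometric mean, small example.** Take LLOQ = 1 and results {below LLOQ, 10, 20, 40}.
- Zero kept: the geometric mean collapses to 0.
- Zero dropped: (10 × 20 × 40)^(1/3) = 8000^(1/3) = 20.0.
- LLOQ/2: (0.5 × 10 × 20 × 40)^(1/4) = 4000^(1/4) = 7.95.

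The same data give three answers.

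**2. General size.** Let G be the geometric mean of the quantifiable results and f the share below LLOQ. With LLOQ/2 the geometric mean is G^(1−f) × (LLOQ/2)^f. With zeros dropped it is G. The ratio is (2G/LLOQ)^f. Check against step 1: (2 × 20)^0.25 = 2.51, and 20.0/7.95 = 2.52, equal apart from rounding.

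| Assumed G (× LLOQ) | f = 10% | f = 30% | f = 50% |
|---|---|---|---|
| 5 | 1.26 | 2.00 | 3.16 |
| 10 | 1.35 | 2.46 | 4.47 |
| 20 | 1.45 | 3.02 | 6.32 |
| 100 | 1.70 | 4.90 | 14.14 |

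The quantifiable mean G cannot lie below LLOQ, so the ratio exceeds 1 whenever f is above zero: the error is always upward.

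**3. Fold rise.** Take LLOQ = 1, baselines {below, below, below, 4} and post-dose results {10, 20, below, 40}.
- Zero recode: the ratios are infinite, infinite, 0/0 and 10. Only the fourth participant is usable.
- LLOQ/2: the ratios are 20, 40, 1 and 10, and GMFR = (20 × 40 × 1 × 10)^(1/4) = 9.46 from all four.

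The two participants with the largest rises are among those lost under the zero rule.

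**4. Seroconversion.** With LLOQ/2, a participant whose baseline is below LLOQ meets the 4-fold criterion at 4 × LLOQ/2 = 2 × LLOQ. With a zero baseline the outcome depends on the code. Written as Y/B ≥ 4, it is undefined. Written as Y ≥ 4B, every participant passes, including one who goes from zero to zero.

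This applies to the fold-rise definition that SAP 4.3 adopts for the interim. The protocol synopsis uses a fixed titer threshold (above 20) for subjects seronegative at baseline, which needs no division by baseline.

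**The case against.** The best defence is that the SAP's exception already covers binding antibodies. Section 7.3.1.1, which governs those data, calls them titers. Section 5 plans geometric means for titers only, so a narrow meaning would leave binding assays with no geometric mean there. Section 7.2 gives one GMT and one GMFR formula for assay results generally, and no separate GMC formula. The evident purpose of the exception is to make log-scale summaries computable, and a reading that defeats it for three assays is the less natural one. The analyses are secondary and descriptive. Double programming and senior review (SAP 5.1) would make widespread missing fold rises conspicuous.

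Much of this stands. A reader might infer that the SAP sends binding results to zero. The documents do not support that as a fact: it is one literal reading, and LLOQ/2 is a plausible intended one. A reader might also infer that the final analysis will use zeros. That goes too far, because the protocol defers to a final SAP not supplied here.

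The defence does not remove the conflict inside the protocol. Nor does it settle the SAP wording: double programming may expose two readings of section 5.4, but it cannot say which one was prespecified.

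**Conclusion.** The point holds in two parts of different strength.

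- **Protocol 10.5.6: firm.** A blanket zero recode is incompatible with the GMT and GMFR endpoints. On these documents it is the only rule stated for the final analysis. If the interim's fold-rise seroconversion definition is carried forward, that endpoint is affected too.
- **SAP 5.4: an ambiguity.** The exception names titers in a document that uses the word both narrowly and broadly. Below-LLOQ anti-S, anti-RBD and anti-N concentrations can be read as going to zero or to LLOQ/2.

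If zeros were used and dropped, the geometric mean would be inflated by the factors in the table. Those sizes depend wholly on assumed values of G and f; only the upward direction is general.

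Two further inferences should be resisted. Dropping zeros would not give a responders-only mean: it leaves quantifiable results, whether or not the participant met the response criterion, and for GMFR it can remove strong responders. Seroconversion would not necessarily be missing either: a zero baseline makes it undefined or automatically met, depending on the programming.

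**What to change.** - **SAP 5.4:** state that all antibody results below LLOQ, titers and concentrations alike (pseudovirus, anti-S, anti-RBD, anti-N), are set to LLOQ/2. Giving the LLOQ of each assay would make the rule reproducible.
- **Protocol 10.5.6 or the final SAP:** replace the zero recode with the same rule for antibody data.
- **If the interim has already been run:** confirm from the programs which rule was applied to the binding assays and record it with the results, since SAP 5.1 allows no change to the interim SAP after the data pull.

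The cost is one sentence in each document and, if needed, one check of existing code. No data collection changes.
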